8.4.6. Pregnancy

Female participants who become pregnant after administration of the study intervention may continue the study at the discretion of the investigator.

- Details of all pregnancies in female participants will be collected after the start of study intervention and until EOS.
- If a pregnancy is reported, the investigator will record pregnancy information on the appropriate form and submit it to the sponsor within 24 hours of learning of the female participant pregnancy.
- Any pregnancy complication or elective termination of a pregnancy for medical reasons will be reported as an AE or SAE.
- Abnormal pregnancy outcomes (e.g., spontaneous abortion, fetal death, stillbirth, congenital anomalies, ectopic pregnancy) are considered SAEs and will be reported as such.
- The participant will be followed to determine the outcome of the pregnancy. The investigator will collect follow-up information on the participant/pregnant female partner and the neonate and the information will be forwarded to the sponsor. See [Table 17](#) for reporting timeframes.
- Any poststudy pregnancy-related SAE considered reasonably related to the study intervention by the investigator will be reported to the sponsor as described in [Section 8.4.5](#). While the investigator is not obligated to actively seek this information in former study participants/pregnant female partner, he or she may learn of an SAE through spontaneous reporting.
- Any female participant who becomes pregnant while participating in the study will continue to be monitored after study intervention.

8.4.7. Contact information for reporting SAEs, AESIs and pregnancies.

Study contact for questions regarding SAEs, AESIs, pregnancies and SAEs linked to device deficiencies
Contact GSK's local and/or medical contacts
Contacts for reporting SAEs, AESIs, pregnancies and SAEs linked to device deficiencies
Available 24/24 hours and 7/7 days [contact]

8.4.8. Participant card

The investigator (or designee) must provide the participant/participant's parent(s)/LAR(s) with a "participant card" containing information about the clinical study. The participant/participant's parent(s)/LAR(s) must be instructed to always keep the participant card in their possession for the duration of the study. In an emergency, this card serves to inform the responsible attending physician/LAR/caregiver/family member that the participant is in a clinical study and that relevant information may be obtained by contacting the investigator(s) or their back up.

8.5. Pharmacokinetics

Not applicable to this study.

8.6. Pharmacodynamics

Pharmacodynamics are not evaluated in this study.

8.7. Genetics

Genetics are not evaluated in this study.

8.8. Biomarkers

Biomarkers are not evaluated in this study.

8.9. Immunogenicity assessments

Immunogenicity is described in Section [8.2](#).

8.10. Health economics or medical resource utilization and health economics

Not applicable in this study.

9. STATISTICAL CONSIDERATIONS

9.1. Statistical hypotheses

Statistical hypotheses are associated to the confirmatory primary NI objectives, which will be tested according to the hierarchical testing procedure described in Section 9.3.1. Global type I error is controlled at 2.5% (1-sided).

Table 18 Study objectives and null hypothesis

Objectives	Null hypothesis
	Primary (Part A)

 To demonstrate the NI of the humoral immune response in participants 18-49 YOA at increased risk for RSV disease compared to OA (≥ 60 YOA) for the RSV-A strain after RSVPreF3 OA investigational vaccine administration. 	
 Null hypothesis 1 (H1): The anti-RSV-A GMT ratio RSV-OA (≥ 60 YOA) over RSV-A-AIR (18-49 YOA) is >1.5 or the SRR difference (RSV-OA [≥ 60 YOA]) minus RSV-A-AIR [18-49 YOA]) is $>10\%$ at 1 month post RSVPreF3 OA vaccine administration. This must be rejected in favor of the alternative hypothesis that the GMT ratio is ≤ 1.5 and the SRR difference is $\leq 10\%$.

 To demonstrate the NI of the humoral immune response in participants 18-49 YOA at increased risk for RSV disease compared to OA (≥ 60 YOA) for the RSV-B strain after RSVPreF3 OA investigational vaccine administration. 	
 Null hypothesis 2 (H2): The anti-RSV-B GMT ratio RSV-OA (≥ 60 YOA) over RSV-A-AIR (18-49 YOA) is >1.5 or the SRR difference (RSV-OA [≥ 60 YOA]) minus RSV-A-AIR [18-49 YOA]) is $>10\%$ at 1 month post RSVPreF3 OA vaccine administration. This must be rejected in favor of the alternative hypothesis that the GMT ratio is ≤ 1.5 and the SRR difference is $\leq 10\%$.

A=Adults; AIR=At increased risk; GMT=Geometric mean titer; H1=Null hypothesis 1; H2=Null hypothesis 2; NI=Non-inferiority; OA=Older adults; RSV=Respiratory syncytial virus; SRR=Seroreponse rate; YOA=Years of age.

9.2. Analysis sets

Table 19 Analysis sets

Analysis Set	Definition / Criteria	Analyses Evaluated
Screened Set	All participants who were screened for eligibility.	Study Population
Enrolled Set	All participants who entered the study (who were allocated a treatment number or received study intervention or underwent a post screening study procedure). Note: screening failures (who never passed screening) and participants screened (met eligibility) but never enrolled into the study are excluded from the Enrolled analysis set as they did not enter the study.	Study Population
Exposed Set (ES)	All participants who received the study intervention. Analysis per group is based on the administered intervention.	Study population, Reactogenicity, Safety
Per-Protocol Set (PPS)*	All eligible participants who received the study intervention as per protocol, had immunogenicity results pre- and post-dose, complied with blood draw intervals, without intercurrent conditions that may interfere with immunogenicity and without prohibited concomitant medication/vaccination. Analysis per group is based on the administered intervention.	Immunogenicity

*Contribution of participants to PPS will be defined by timepoint

9.2.1. Criteria for elimination from analyses

If a participant meets one of the criteria mentioned in the Section 5.2.1 (medical conditions) or Section 5.2.2 (concomitant therapy), they may be eliminated from per-protocol analysis.

Participants may be eliminated from the PPS for immunogenicity if, during the study, they incur a condition that has the capability of altering their immune response (intercurrent medical condition) or are confirmed to have an alteration of their initial immune status. Refer to [Definition of Terms](#) for the definition of intercurrent medical conditions.

9.3. Statistical analyses

SAP will include a more technical and detailed description of the statistical analyses described in this section. This section is a summary of the planned statistical analyses of the primary and secondary endpoints. Supportive analyses and demography summaries will be described in the SAP.

9.3.1. Primary endpoints/estimands analysis (Part A)

Primary estimand analysis will be performed on the Per-Protocol Set (PPS) for participants in Part A.

RSV-A and RSV-B neutralizing group GMT ratio at 1 month after the RSVPreF3 OA vaccine administration will be computed for RSV-OA (≥ 60 YOA) cohort over RSV-A-AIR (18-49 YOA) cohort, with 95% CI, using an [CCI](#) on log10-transformed titers for each neutralization assay. The model will include the group RSV-OA (≥ 60 YOA) and RSV-A-AIR (18-49 YOA) and the baseline log10-transformed titer as covariate.

RSV-A and RSV-B neutralizing group SRR differences at 1 month after the RSVPreF3 OA vaccine administration will be computed for RSV-OA (≥ 60 YOA) cohort minus RSV-A-AIR (18-49 YOA) cohort, with 95% CI. The 95% CI will be derived using the method of [CCI](#) 1985. SRR is defined as the proportion of participants having a fold increase in neutralizing titers (post-study intervention administration over pre-study intervention administration) ≥ 4 .

Missing data will not be imputed.

9.3.1.1. Success criteria for non-inferiority and testing sequence

In order to control the global type I error at 2.5% (1-sided), the primary objective will be assessed using a hierarchical testing. NI will be first tested for RSV-A strain and, only if NI has been demonstrated, will the NI be tested for RSV-B strain.

NI for RSV-A strain will be claimed to be successful if the upper limit of the 95% CI for the RSV-A neutralizing group GMT ratio will be ≤ 1.5 and the upper limit of 95% CI for the RSV-A neutralizing group SRR difference will be $\leq 10\%$.

NI for RSV-B strain will be claimed to be successful if NI has been demonstrated for RSV-A strain and if the upper limit of the 95% CI for the RSV-B neutralizing group GMT ratio will be ≤ 1.5 and the upper limit of 95% CI for the RSV-B neutralizing group SRR difference will be $\leq 10\%$.

9.3.2. Secondary endpoints/estimands analyses

The estimand analysis for immunogenicity will be performed on the PPS, for participants in Part A.

For each timepoint with blood sample collection for humoral immune response and for RSV-A/B neutralizing titers, the following analysis will be performed by group:

- Percentage of participants with neutralizing titers equal to or above the technical assay cut-off and their exact 95% CI will be tabulated.
- GMTs and their 95% CI will be tabulated and represented graphically.
- Distribution of neutralizing titers will be displayed using reverse cumulative curves.
- MGI, i.e., geometric mean of ratios of neutralizing titers of post vaccination time point over pre-vaccination (Day 1), will be tabulated with 95% CI.
- SRR and 95% CI will be tabulated.

The estimand analysis for safety will be performed on the ES, for participants in Parts A and Part B. Descriptive analysis by group will be summarized as follows:

- Percentage of participants reporting each solicited administration site event (any grade, Grade 3 and resulting in medically attended visit) with onset within 4 days after study intervention administration (i.e., the day of study intervention administration and 3 subsequent days).
- Percentage of participants reporting each solicited systemic event (any grade, Grade 3 and resulting in medically attended visit) with onset within 4 days after study intervention administration (i.e., the day of study intervention administration and 3 subsequent days).
- Percentage of participants reporting unsolicited AEs within 30 days after study intervention administration (i.e., the day of study intervention administration and 29 subsequent days) by MedDRA Primary System Organ Class (SOC), High Level Term (HLT) and Preferred Term (PT). Similar tabulation will be done for Grade 3 unsolicited AEs, for any causally related unsolicited AEs, for Grade 3 causally related unsolicited AEs and for unsolicited AEs resulting in a medically attended visit.

- Percentage of participants reporting SAEs and AESIs (including pIMDs and AF) after study intervention administration (Day 1) up to study end (6 months after study intervention administration) by MedDRA Primary SOC, HLT and PT.
- Percentage of participants reporting SAEs and AESIs (including pIMDs and AF) related to study intervention administration after study intervention administration (Day 1) up to study end (6 months after study intervention administration) by MedDRA Primary SOC, HLT and PT.
- Percentage of participants reporting any fatal SAEs after study intervention administration (Day 1) up to study end (6 months after study intervention administration).

9.4. Interim analyses

9.4.1. Sequence of analysis

The analyses will be performed stepwise:

- **Day 31 (Part A):** A first analysis will be performed on all immunogenicity, reactogenicity and safety data available and as clean as possible, when data for at least primary and secondary endpoints up to Visit 2 (Day 31) are available for all participants in Part A. This analysis will be considered as final for the primary endpoints.
- **Month 6 (Part A):** If required, a safety analysis can be performed when safety data up to Month 6 are available and as clean as possible, for all participants in Part A.
- **Day 31 (Part B):** If required, a safety analysis can be performed when safety data up to Visit 2 (Day 31) are available and as clean as possible, for all participants in Part B. This analysis may be combined with Month 6 safety analysis for Part A.

Month 6 (Part A): If required an immunogenicity analysis can be performed when all data for secondary endpoints up to study conclusion (Visit 3, Month 6) are available and as clean as possible, for all participants in Part A.

- An **EOS** analysis will be performed when all immunogenicity and safety data up to study conclusion (Visit 3/Contact, Month 6) will be available for all participants in Part A and Part B.
- If the data of different analyses become available around the same timepoint, these analyses can be combined into one analysis.

9.5. Pre-dose sample size determination

The target sample size for the study is approximately 850 participants for Part A: 425 participants in Cohort 1 (RSV-A-AIR [18-49 YOA group]) and 425 participants in Cohort 2 (RSV-OA [≥ 60 YOA group]), to obtain at least 722 evaluable participants (361 participants in the RSV-A-AIR [18-49 YOA] cohort and 361 participants in the RSV-OA [≥ 60 YOA] cohort) for the evaluation of the primary objectives, assuming that approximately 15% of the enrolled participants will not be evaluable.

Participants who withdraw from the study will not be replaced.

The power to demonstrate the primary NI objectives following the hierarchical testing procedure described in Section 9.3.1 is presented in Table 20.

Table 20 Power for primary objectives of non-inferiority of the humoral immune response after RSVPreF3 OA vaccine between the RSV-A-AIR (18-49 YOA) Cohort 1 to RSV-OA (\geq 60 YOA) Cohort 2 for 361 evaluable participants per group

Objective	Standard deviation (SD) of log ₁₀ titers / SRR (%)	Non-inferiority margin	Type II Error	Power ¹
NI for RSV-A strain				
GMT RSV-A	SD=0.45	1.5	0.05	99.95%
SRR RSV-A	SRR=81.6% ²	10%	6.92	93.08%
Global power for RSV-A strain				93%
NI for RSV-B strain				
GMT RSV-B	SD=0.45	1.5	0.05	99.95%
SRR RSV-B	SRR=78.7% ²	10%	9.56	90.44%
If non-inferiority is demonstrated for RSV-A, global power for RSV-B strain				90%

NI=Non-inferiority; SRR=Seroresponse rate; GMT=Geometric mean titer; RSV=Respiratory syncytial virus

¹Pass 2019 1-sided alpha=2.5% for each endpoint (GMT ratio and SRR difference), two-Sample T-Tests for Non-Inferiority assuming equal variance for group GMT ratios and ^{CCI} for Non-Inferiority tests for group SRR difference, Non-inferiority limit=0.176 (=log₁₀(1.5)) for group GMT ratios

²Reference from RSV OA=ADJ-006

For the evaluation of reactogenicity and safety, the sample size of 1025 participants in combined Cohorts 1 and 3 (RSV-A-AIR group) has 64% and 87% probability of observing at least one vaccinated participant with AE if the true AE incidence rate is 0.1% and 0.2% respectively. This probability increases to at least 95% for true AE incidence rates \geq 0.3%.

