5. SAMPLE SIZE DETERMINATION

The target sample size for the study is approximately 850 participants: 425 participants in Cohort 1 (RSV-A-AIR [18-49 YOA group]) and 425 participants in Cohort 2 (RSV-OA [≥ 60 YOA group]), to obtain at least 722 evaluable participants (361 participants in the RSV-A-AIR [18-49 YOA] cohort and 361 participants in the RSV-OA [≥ 60 YOA] cohort) for the evaluation of the primary objectives, assuming that approximately 15% of the enrolled participants will not be evaluable.

Participants who withdraw from the study will not be replaced.

The power to demonstrate the primary NI objectives following the hierarchical testing procedure described in Section 2.1 is presented in [Table 6](#).

Table 6 Power for primary objectives of non-inferiority of the humoral immune response after RSVPreF3 OA vaccine between the RSV-A-AIR (18-49 YOA) Cohort 1 to RSV-OA (≥ 60 YOA) Cohort 2 for 361 evaluable participants per group

Objective	Standard deviation (SD) of log10 titers / SRR (%)	Non-inferiority margin	Type II Error	Power ¹
NI for RSV-A strain				
GMT RSV-A	SD=0.45	1.5	0.05	99.95%
SRR RSV-A	SRR=81.6% ²	10%	6.92	93.08%
Global power for RSV-A strain				93%
NI for RSV-B strain				
GMT RSV-B	SD=0.45	1.5	0.05	99.95%
SRR RSV-B	SRR=78.7% ²	10%	9.56	90.44%
If non-inferiority is demonstrated for RSV-A, global power for RSV-B strain				90%

NI=Non-inferiority; SRR=Seroresponse rate; GMT=Geometric mean titer; RSV=Respiratory syncytial virus

¹Pass 2019 1-sided alpha=2.5% for each endpoint (GMT ratio and SRR difference), two-Sample T-Tests for Non-Inferiority assuming equal variance for group GMT ratios and Miettinen and Nurminen for Non-Inferiority tests for group SRR difference, Non-inferiority limit=0.176 (=log10(1.5)) for group GMT ratios

²Reference from RSV OA=ADJ-006

For the evaluation of reactogenicity and safety, the sample size of 1025 participants in combined Cohorts 1 and 3 (RSV-A-AIR group) has 64% and 87% probability of observing at least one vaccinated participant with AE if the true AE incidence rate is 0.1% and 0.2% respectively. This probability increases to at least 95% for true AE incidence rates $\geq 0.3\%$.

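### Does the 90% power quoted for RSV-B overstate the chance of meeting both primary objectives?

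*Protocol*

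**What the plan says.** Protocol 9.5 presents Table 20 with the sentence "The power to demonstrate the primary NI objectives following the hierarchical testing procedure described in Section 9.3.1 is presented in Table 20". SAP Section 5 opens its copy, Table 6, in the same way: "The power to demonstrate the primary NI objectives following the hierarchical testing procedure". Both tables give GMT power of 99.95% for each strain, and SRR power of 93.08% for RSV-A and 90.44% for RSV-B. The two summary rows are 93% for RSV-A and 90% for RSV-B, and the second is labelled "If non-inferiority is demonstrated for RSV-A, global power for RSV-B strain".

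The testing order is fixed in Protocol 9.3.1.1: "NI for RSV-B strain will be claimed to be successful if NI has been demonstrated for RSV-A strain", and the RSV-B criteria must then be met as well. Protocol 9.1 adds: "Global type I error is controlled at 2.5% (1-sided". Neither document gives the probability of succeeding on both strains, or any assumption about the correlation between strains.

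**The concern.** Under a fixed sequence, the unconditional power for the second hypothesis is the probability that both hypotheses are rejected. The introductory sentence promises power under the hierarchy, yet the RSV-B summary row is built only from the RSV-B type II errors; no RSV-A error enters it. A reader who takes the two summary percentages at face value sees a 7% to 10% risk per objective. The risk of missing at least one could be near 16% or 17%. Both strains are primary objectives, so if the headline figure were inflated, ethics committees and regulators would be judging a less secure design than the one described.

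**Working it through.** **Inputs (Protocol 9.5, repeated in SAP Section 5).** 361 evaluable participants per cohort (425 × 0.85 = 361.25); one-sided alpha 2.5% for each endpoint; SD 0.45 on log10 titers; GMT ratio margin 1.5 (0.176 on log10); SRR 81.6% for RSV-A and 78.7% for RSV-B; SRR margin 10 percentage points; Miettinen and Nurminen method for SRR (named in the SAP). The documents do not state the true group difference. I assume a GMT ratio of 1 and an SRR difference of 0, which reproduces the table.

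**Step 1: reproduce the plan's figures.**
- GMT: SE = 0.45 × √(2/361) = 0.0335. Power = Φ(0.1761/0.0335 − 1.96) = Φ(3.30) = 99.95%. Stated: 99.95%.
- SRR RSV-A, unpooled normal approximation: SE = √(2 × 0.816 × 0.184/361) = 0.0288. Power = Φ(0.10/0.0288 − 1.96) = 93.4%. Exact enumeration of the Miettinen-Nurminen test gives 93.2%. Stated: 93.08%.
- SRR RSV-B: SE = √(2 × 0.787 × 0.213/361) = 0.0305. Power = 90.7% by the approximation and 90.6% by enumeration. Stated: 90.44%.
- Strain level: 0.9308 × 0.9995 = 93.0% for RSV-A and 0.9044 × 0.9995 = 90.4% for RSV-B. Adding type II errors gives the same: 100 − 0.05 − 6.92 = 93.03 and 100 − 0.05 − 9.56 = 90.39.

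The table is arithmetically sound. Its 90% is the power of the RSV-B tests taken on their own.

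**Step 2: power for both strains.**
- Lower bound under any dependence: 100 − (0.05 + 6.92 + 0.05 + 9.56) = 100 − 16.58 = 83.4%.
- Independence: 0.9303 × 0.9039 = 84.1%.
- Upper limit: joint power cannot exceed the RSV-B power, about 90.4%.

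**Step 3: the effect of correlation.** The documents give none, so the range is shown as an assumption. The two SRR tests are treated as bivariate normal with the table's marginal powers, and the result is multiplied by 0.9995². Conditional power is joint power divided by 93.03%.

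| Correlation between SRR tests | Power for both strains | Power for RSV-B given RSV-A success |
|---|---|---|
| 0 | 84.1% | 90.4% |
| 0.5 | 85.8% | 92.3% |
| 0.7 | 87.0% | 93.5% |
| 0.9 | 88.8% | 95.4% |
| towards 1 | about 90% | about 97% |

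The risk of missing at least one strain is therefore 15.9% at independence, 14.2% at correlation 0.5, 11.2% at 0.9 and roughly 10% in the limit. Its worst case is 16.6%.

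**Step 4: compare with the row label.** The label describes the right-hand column. The printed 90% equals that column at independence and lies below it at every positive correlation. RSV-A and RSV-B titers are measured in the same Part A participants at the same visits (Protocol 8.2.3), with the same assay format (Protocol 10.2.1), after the same vaccine. Positive correlation is therefore the more plausible case.

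**The case for a change.** The best argument for a change is that the row label and the introductory sentence cannot both be exact. If 90% is the conditional power, the strains are independent and the power under the hierarchy is 84%. If 90% is the power under the hierarchy, the correlation is perfect and the conditional power is about 97%. In between, the printed figure is neither. Adding one row would spare every reader the derivation.

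The logic is correct, and it stands that joint power is missing from both documents. It does not show that a stated figure misleads. Giving the power for step one, and then for step two once step one has passed, is a natural way to describe a sequential procedure. The condition is printed in the row itself, and a reader can multiply 93% by 90% to get 83.7%. Treated as the conditional power it is labelled to be, the 90% errs on the cautious side under positive correlation.

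Nor is joint power a commitment of this plan. Protocol 9.3.1.1 lets RSV-A be claimed on its own criteria whether or not RSV-B follows. No rule defines success as both strains, and no overall power target is set. Protocol 4.2 says only that efficacy can potentially be inferred from non-inferiority.

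**Conclusion.** No change to the plan is needed. The documents leave out a summary figure; they do not misstate one. The power for both strains is at least about 83%, 84% under independence and up to about 90% under strong positive correlation. This rests on the table's own SRR and SD inputs, on no true difference between cohorts, and on a correlation that the documents do not give. It would be wrong to report 83% to 84% as the actual joint power, since that is the worst-case or independence value.

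Stating the range would be a harmless courtesy to readers, but nothing depends on it. The 425 per cohort, the margins, the control of type I error, the success criteria and the interpretation of any result stay the same.

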10. SUPPORTING DOCUMENTATION AND OPERATIONAL CONSIDERATIONS

10.1. Appendix 1: Regulatory, ethical, and study oversight considerations

10.1.1. Regulatory and ethical considerations

- This study will be conducted in accordance with the protocol and with the following:
 - Consensus ethical principles derived from international guidelines including the Declaration of Helsinki and CIOMS international ethical guidelines

- Applicable ICH GCP guidelines
- Applicable laws and regulations
- The protocol, protocol amendments, ICF, IB, and other relevant documents (e.g., advertisements) must be submitted to an IRB/IEC by the investigator and reviewed and approved by the IRB/IEC before the study is initiated.
- Any amendments to the protocol will require IRB/IEC approval before implementation of changes made to the study design, except for changes necessary to eliminate an immediate hazard to study participants.
- Protocols and any substantial amendments to the protocol will require health authority approval prior to initiation except for changes necessary to eliminate an immediate hazard to study participants.
- The investigator will be responsible for the following, as applicable:
 - Providing written summaries of the status of the study to the IRB/IEC annually or more frequently in accordance with the requirements, policies, and procedures established by the IRB/IEC
 - Notifying the IRB/IEC of SAEs or other significant safety findings as required by IRB/IEC procedures
 - Providing oversight of the conduct of the study at the site and adherence to requirements of 21 CFR, ICH guidelines, the IRB/IEC, European regulation 536/2014 for clinical studies (if applicable), and all other applicable local regulations

